## Sample size

Group size was calculated using Lehr's formula to have a power of 80%, considering a 5% level of significance, and a difference of 13 MFI in the CD4+ T cells between the two group means and assuming a combined standard deviation of 10 MFI (PMID: 18341999).

**EO:** We expect to answer the question whether zinc nutritional status before SARS-CoV2 infection determines COVID-19 progression. Moreover, we expect to understand the correlation between serum zinc levels and disease progression.

**D3:** Scientific communication addressed to physicians and public health decision makers describing the potential benefits of using zinc supplementation as a prophylactic strategy against severe COVID-19.

### **3 To characterize novel zinc homeostasis reporters upon SARS-CoV2 infection**

**(Subproject 2)** We will run RT-PCR for the 14 Zip and 10 ZnT transporters and for MT1 and MT2. The expression analysis will be correlated to serum zinc levels measured.

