### **Zinc and inflammation**

ZD is known to be associated with proinflammatory responses at infection, showing higher ROS production and inflammatory markers (6,7). An imbalance in cytokine production by cells of both innate and adaptive immunity has also been reported.

Concretely, ZD is associated with higher levels of IL-6, IL-1beta and TNF-alfa (6). In this scenario, zinc supplementation has been shown to decrease the incidence of infection, inflammatory cytokines, including IL-6, and oxidative stress markers in elderly individuals (7,8). Moreover, zinc supplementation has been shown to balance immune responses (9). Remarkably, IL-6 is a key player in COVID-19 patients by triggering severe lung damage during SARS-CoV-2 infection.

Sustained IL-6 promotes immune-mediated lung damage and macrophage activation syndrome (10). Nutritional zinc status and IL-6 are highly interconnected. Thus, IL-6 can reduce zinc bioavailability promoting internalization in hepatocytes and the expression of zinc chelators (11). On the other hand, zinc decreases IL-6 production via inhibition of STAT-3 pathway (12). Our study with COVID-19 patients showed a negative correlation between serum zinc levels and IL-6 production (13). Both parameters were robustly associated with COVID-19 progression. This data is in agreement by another observational study with a smaller cohort (14). However the cause-effect association between zinc status and inflammation markers in COVID-19 patients is not yet clear given the observational nature of the studies (13,14).

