### **Task 1.1.1 Visits and sample collection**

1.- Visit 1. Screening. Randomization. Baseline. Phase / Visit 0 or 1 ( Day 1 or up to 1 day  
Prior to Baseline/Randomization; In Person)

Visit performed at admission (+1). Written informed consent obtained. Medical history.  
Vital signs assignment. Clinical labs (CBC, CMP, CRP, ferritin, D-dimer,IL-6, zinc)

2.-Visit 2 / Week 1 (Day 7  $\pm$  2 days)

A complete record of AEs and concomitant therapies will be taken into account. 3.-

Visit 3 / Week 2 (Day 14  $\pm$  2 days), End of Treatment

A complete vital sign assessment (sitting blood pressure, heart rate, respiratory rate, O2  
sat, and oral temperature) review and record AEs and concomitant therapies, clinical  
labs (stated above) and PBMCs. Collect blood samples for future studies.

4.-Visit 4 / End of Study (Day 28  $\pm$  4 days)

Clinical labs (stated above) and PBMCs. Collect blood samples for future studies.

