#### **Task 3.1 Characterization of machinery for cellular zinc handling in PBMCs from COVID- 19 patients**

We will study the expression in PBMCs from COVID-19 patients enrolled in the clinical trial (objective 1.1) in both groups at admission and at 2 weeks.

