**Task 3.2 Characterization of machinery for cellular zinc handling in PBMCs from SARS-CoV-2 infected mice. from mice**

We will study the expression in PBMCs from SARS-CoV-2 infected mice at 7 days post infection (objective 2.1) in the three groups of mice (deficient, adequate and supplemented diet).

**EO:** Zinc plasma levels are very dependent on inflammatory signalling. We expect to find certain genes differentially regulated depending on the nutritional zinc status and COVID-19 progression.

**D4:** A novel and reliable diagnostic tool in the hospitals to check zinc nutritional status and define therapeutic strategies with COVID-19 patients and for other infectious diseases.

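### Objective 3 relates PBMC gene expression in patients only to serum zinc, without accounting for inflammation, so that correlation alone cannot support D4's diagnostic tool for zinc nutritional status

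*Combined protocol and SAP*

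**What the plan says.** The opening paragraph of Objective 3 sets the panel, "We will run RT-PCR for the 14 Zip and 10 ZnT transporters and for MT1 and MT2", and then the analysis: "The expression analysis will be correlated to serum zinc levels measured". No other analysis, cut-off, accuracy measure, validation sample or multiplicity rule is given for this objective.

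Task 3.1 takes patient expression from the trial "in both groups at admission and at 2 weeks". Task 3.2 takes mouse expression at 7 days after infection in three diet groups (deficient, adequate, supplemented).

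The expected outcome under Task 3.2 opens with "Zinc plasma levels are very dependent on inflammatory signalling" and anticipates genes that are regulated differently according to nutritional zinc status and disease course. Deliverable D4 is then "A novel and reliable diagnostic tool in the hospitals to check zinc nutritional status".

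Three other places bear on this:

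- The background section on zinc and inflammation says that "IL-6 can reduce zinc bioavailability promoting internalization in hepatocytes and the expression of zinc chelators". It reports a negative correlation between serum zinc and IL-6 in the team's own cohort, without a coefficient, and also says that zinc lowers IL-6 production.
- The limitation at the end of the Statistical analysis section reads a null trial result as meaning that low zinc is a consequence of inflammation.
- Task 1.1.1 includes CRP, ferritin, IL-6 and zinc in the clinical labs at baseline. The Week 2 entry lists "clinical labs (stated above) and PBMCs. Collect blood samples for future studies", and the Day 28 entry lists the same items.

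**The concern.** A new marker of zinc status is worth having because serum zinc is disturbed by inflammation. If candidate genes are judged in acutely ill patients by their correlation with serum zinc, a gene can score well in two ways: it reflects zinc status, or it responds to the same inflammatory signals that move serum zinc. The stated analysis does not tell these apart. A larger sample or a multiplicity correction would not help, because the second route produces a real correlation, not a chance one.

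At stake is D4. A gene chosen for the second reason would share the weakness of the test it is meant to improve on, and a tool built on it could label inflamed patients as zinc-deficient.

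**Working it through.** Objective 3 states no sample size, power, alpha or accuracy target, so there is no figure of the plan's to reproduce. The check asks how easily a gene with no link to zinc status could be selected.

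**Inputs from the documents**

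- Genes: 14 + 10 + 2 = 26 (Objective 3).
- Patients: 60 randomised with 10% dropout (Determination of sample size), so 60 × 0.9 = 54, or 27 per arm, at 2 weeks.
- Alpha 0.05 (same section; sidedness not stated, two-sided assumed).
- Sign of the zinc to IL-6 correlation: negative (Zinc and inflammation).
- Mice: 21 per group in Task 2.1; 10 per group sacrificed at each time point in Task 2.2. Task 3.2 refers to objective 2.1, but the planned day 7 sacrifice with PBMCs is in Task 2.2, so both sizes are shown.

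**Assumed:** the sizes of the zinc-inflammation and gene-inflammation correlations, each from 0.3 to 0.7.

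**Step 1: induced correlation.** For a gene related to serum zinc only through inflammation, r(gene, zinc) = r(gene, inflammation) × r(zinc, inflammation). With 0.5 and −0.5 this is −0.25.

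**Step 2: chance of significance.** By Fisher's z, the chance is Φ(atanh|r|·√(n−3) − 1.96) plus a negligible or small opposite tail. For |r| = 0.25 and n = 54: atanh(0.25) = 0.255, √51 = 7.141, product 1.82; Φ(1.82 − 1.96) = Φ(−0.14) ≈ 0.45.

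Results at n = 54, unadjusted, with Bonferroni for 26 genes in brackets:

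| Size of zinc-inflammation r | gene r = 0.3 | gene r = 0.5 | gene r = 0.7 |
|---|---|---|---|
| 0.3 | 10% (1%) | 19% (2%) | 33% (6%) |
| 0.5 | 19% (2%) | 45% (10%) | 74% (31%) |
| 0.7 | 33% (6%) | 74% (31%) | 97% (77%) |

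At n = 60 the unadjusted diagonal is 10%, 49% and 98%.

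**Step 3: chance findings.** With no true relation at all, 26 tests at 0.05 give 26 × 0.05 = 1.3 expected false positives and a chance of at least one of 1 − 0.95^26 = 74%, taking the tests as independent.

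**Step 4: what adjustment does.** The numerator of the partial correlation given inflammation is r(gene, zinc) − r(gene, inflammation) × r(zinc, inflammation). For the gene in Step 1 this is zero, so adjustment removes the artefact if inflammation is well measured and acts on zinc in one direction only. The background describes influence in both directions, so adjustment may also remove part of a genuine zinc signal.

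**Step 5: what the existing contrasts can detect.** Standardised difference at 80% power = (1.96 + 0.84) × √(2/m), with m per group:

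| Contrast | m | Two-sided 0.05 | 0.05/26 |
|---|---|---|---|
| Randomised arms | 27 | 0.76 SD | 1.07 SD |
| Diet groups, Task 2.1 size | 21 | 0.86 SD | 1.22 SD |
| Diet groups, Task 2.2 size | 10 | 1.25 SD | 1.76 SD |

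These make no allowance for any precision gained by adjusting for admission expression.

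**The case against.** A reader might infer that the marker is to be validated against serum zinc, that Objective 3 has no means of separating zinc status from the acute-phase response, and that it would therefore select inflammation markers. The documents do not support this reading:

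- The plan says that expression will be correlated with serum zinc. It describes no validation step of any kind.
- Two planned contrasts do not rest on serum zinc: both randomised groups supply PBMCs, and the mouse groups are defined by diet. The expected outcome speaks of nutritional zinc status.
- Acute infection does not describe the mouse measurement, because Task 2.1 takes serum zinc before virus challenge. Some patients may also be past the acute phase by 2 weeks.
- No coefficient is given, and the table above runs from unlikely to near certain. The word has to be could, not would.

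The opposing case has further points. The section on cellular zinc homeostasis already presents leukocyte metallothionein expression as among the most reliable measures of body zinc, so MT1 and MT2 do not depend on the new correlation alone. The authors plainly know the limits of serum zinc; it reads as their motive. And this is exploratory laboratory work outside the trial endpoints.

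All of that stands, and it narrows the point without removing it. The plan does not say that either contrast will be used to choose a marker, and the one analysis it does state for patients ignores inflammation. Knowing the limitation is not the same as handling it. The prior support covers 2 of the 26 genes.

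**Conclusion.** The point holds in limited form. In patients, the only stated analysis for Objective 3 is a correlation with serum zinc that takes no account of inflammation, although the plan says serum zinc depends on it and collects IL-6 and CRP. That correlation could select inflammation-driven genes, and on its own it does not support a reliable diagnostic tool for nutritional status.

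The size is uncertain. An inflammation-only gene has about a 10% to 97% chance of reaching significance at n = 54 (1% to 77% with Bonferroni), resting on assumed correlations of 0.3 to 0.7, a two-sided 0.05 level and a single inflammatory pathway. The conclusion about D4 does not depend on where in that range the truth lies, because the plan offers no way to tell the two kinds of gene apart using this correlation. The primary, secondary and safety endpoints are unaffected. This is a low-cost improvement to a laboratory objective.

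**What to change.** In the opening paragraph of Objective 3:

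1. Name as the main evidence for a zinc-status marker (a) the comparison of expression between randomised arms at Week 2, adjusted for admission expression, and (b) the comparison across the Task 3.2 diet groups. State the number of mice per group, and how the 26 genes are handled for multiplicity.
2. Report the serum zinc correlation both unadjusted and adjusted for same-visit IL-6 and CRP, as supporting evidence only. Neither version is decisive, because zinc may itself lower IL-6.
3. Reword D4 to candidate markers supported by at least one of the contrasts in item 1.
4. List PBMCs at Visit 1 in Task 1.1.1. Task 3.1 needs them at admission, but that visit's list does not mention them.

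Day 28 expression is optional, if PBMC material remains after the T-cell memory assays planned for that visit in Task 1.2.2.

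Cost: items 1 to 3 use data already planned and change only text and analysis; Day 28 RT-PCR would be extra laboratory work. Fewer genes will qualify, and a true marker with a moderate effect may be missed, since the contrasts detect only about 0.76 SD (27 per arm) or 1.25 SD (10 mice per group) before multiplicity. Neither contrast is perfect: the arm difference is not purely nutritional if zinc changes inflammation, all Task 3.2 mice are infected, and mouse results cannot set a cut-off for patients. These limits are why D4 should claim candidates rather than a finished tool.

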### **Zinc in T lymphocytes activation and exhaustion**

Several studies have indicated that T cells have a role both in the early immune response against SARS-CoV-2 and that a functional memory is generated (19). In this context, zinc is known to affect T lymphocyte maturation, differentiation and cytokine production (2,4,7). Activated T cells are known to increase zinc content (20). On the one hand, zinc has been shown to be required for the correct TCR signalling by modulating Lck and Zap-70 activity (20). Our team has demonstrated that zinc positively potentiates the three main signalling pathways, AP-1, NF- $\kappa$ B and NFAT1 (21). In addition we have described that the knock down of Zip6, a zinc transporter up regulated early during cell activation, alters zinc entry and dramatically impairs activation of Jurkat T cells (21). Moreover, recent studies on CD8+ T cell dysfunction during cancer and chronic infections have started to elucidate the transcriptional pathways involved in this phenomenon and zinc homeostasis has emerged again as a key element. Thus, metallothioneins 1 and 2 levels and zinc dependent transcription factors are differentially expressed in exhausted CD8+ cells (22,23,24). Nonetheless, there are no studies investigating whether zinc supplementation/chelation might directly affect the CD8+ dysfunctional profile and how these learnings could be translated into novel therapeutic approaches for these diseases including the current COVID-19 pandemic.

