#### **Task 1.2.2 Assessment of antiviral T-cell responses in COVID-19 patients**

We will use PBMC from COVID-19 patients enrolled in the clinical trial described in objective 1.1 in both groups. We will evaluate T cell responses using intracellular staining and flow cytometry. Subtype population (CD3, CD4, CD8), activation degree (IL-2, INF $\gamma$ , perforin), exhaustion (PD-1, Tim-3) and memory (CD45RO and CD62L) markers will be evaluated using panels of tagged antibodies. We will stimulate T-cells using a commercial pool of overlapping spike peptides of SARS-CoV2. We will study activation degree and exhaustion at admission and at 2 weeks. We will evaluate memory at 28 days post admission.

**EO:** We expect to know whether zinc supplements might strengthen humoral and cellular adaptive immunity in COVID-19 patients. This will be of special interest for immunologists and pharma companies

**D2:** Publication describing the results obtained in the clinical trial with COVID-19 patients and the influence of zinc supplementation in their immune response

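### Expression of 26 zinc-handling genes in PBMCs is correlated with serum zinc without regard to cell mix, cell state or inflammation, so a disease-state marker can be mistaken for a zinc-status reporter

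*Combined protocol and SAP*

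**What the plan says.** Objective 3 (zinc homeostasis reporters) lists the targets: "We will run RT-PCR for the 14 Zip and 10 ZnT transporters and for MT1 and MT2", which is 26 genes. The analysis is a single sentence: "The expression analysis will be correlated to serum zinc levels measured". Task 3.1 fixes the material and timing: "expression in PBMCs from COVID-19 patients enrolled in the clinical trial (objective 1.1) in both groups at admission and at 2 weeks". Task 3.2 repeats the assay in infected mice at day 7 under three assigned diets. Deliverable D4 is "A novel and reliable diagnostic tool in the hospitals to check zinc nutritional status", to be used also in defining treatment strategies.

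Neither Objective 3 nor the Statistical analysis section names a sorting step, a covariate or a model for these data.

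Three statements elsewhere bear on the interpretation:
- The background on T lymphocytes describes "Zip6, a zinc transporter up regulated early during cell activation", and says MT1 and MT2 levels differ in exhausted CD8+ cells.
- The expected-outcome note under Task 3.2 says plasma zinc depends strongly on inflammatory signalling.
- The Preliminary results report that low serum zinc went with higher IL-6 and CRP at admission.

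Useful data are already planned. Task 1.2.2 measures CD3, CD4 and CD8 subsets, activation, and exhaustion (PD-1, Tim-3) by flow cytometry. Task 1.1.1 lists CBC, CRP and IL-6 alongside zinc. Nothing connects them to the expression analysis.

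**The concern.** PBMCs are a mixture of cells. With no separation step, the natural reading is that RT-PCR returns an average over the mixture. That average moves if the proportions or the activation of the cells change, even when zinc handling within each cell does not. If serum zinc also falls with inflammation, sicker patients can have lower zinc and different PBMC expression for reasons unrelated to nutritional zinc. A simple correlation cannot separate these explanations.

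What is at stake is D4. A gene chosen because it tracks inflammation or a cell subset would repeat the weakness of serum zinc that the plan itself acknowledges, and would then be offered as a test of nutritional status.

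**Working it through.** Objective 3 states no sample size, effect size or error rate, so there is no planned figure to reproduce.

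**1. What the documents establish.** At least Zip6, MT1 and MT2 vary with cell state (T-lymphocyte background), and serum zinc varies with inflammation (Task 3.2; Preliminary results). The documents do not give PBMC proportions, how these change over the illness, expression ratios between blood cell types, or the correlation of any of these with serum zinc. Those inputs are assumed below.

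**2. Apparent change from composition alone.** Let one cell type express the gene k times as strongly as the rest, with constant expression per cell. If its share goes from a to b, the apparent fold fall is (a·k + 1 − a)/(b·k + 1 − b). With assumed a = 0.40 and b = 0.20:
- k = 2: 1.4/1.2 = 1.17
- k = 5: 2.6/1.8 = 1.44
- k = 10: 4.6/2.8 = 1.64

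**3. False-positive rate of the simple correlation.** From the plan: 60 patients and 10% dropout, so 60 × 0.9 = 54. Assumed: a cell fraction m with mean 0.20 and SD 0.08; correlation r between m and serum zinc; expression ratio F between the two cell types; assay noise of 0.3 log2 units. Bulk log2 expression is log2[(1 − m) + F·m] plus noise, with no zinc effect in any cell. Share of Pearson tests significant at 5% (2,000 replicates per setting, n = 54):

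| r | F = 1 | F = 2 | F = 5 | F = 10 |
|---|---|---|---|---|
| −0.2 | 4.3% | 6.2% | 14.9% | 21.3% |
| −0.4 | 4.8% | 14.6% | 47.6% | 66.5% |
| −0.6 | 4.3% | 25.9% | 85.2% | 95.4% |

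Adjusting for the mixture term gives 4.0% to 5.3% throughout. With n = 60 the highest unadjusted rate is 97.5%, and adjusted rates are 4.5% to 5.9%. The adjusted figures are a best case, because the simulation knows the mixture exactly and the trial would not.

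A second set of assumptions (mean share 30%, SD 10 points, noise 0.5 log2 units, r from −0.3 to −0.5, ratio 2 to 10, n = 54) gives 7.7% to 61.1% unadjusted.

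**4. Comparison with a detectable signal.** For 80% power at two-sided 5%, the smallest detectable correlation with n = 54 is tanh[(1.96 + 0.8416)/√51] = 0.37. In the table's settings with F from 2 to 10, composition alone produces mean correlations from −0.06 to −0.46. The artefact can therefore be negligible or as large as the signal sought.

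**5. The between-arm comparison is different.** Allocation is 1:1 at random, so cell mix is balanced in expectation unless zinc changes it. Adjusting for week-2 cell state can add bias. Suppose activation is M = d·A + S + e₂ and the gene is Y = S + e₁, where A is arm and S is severity, so that zinc has no effect on the gene. Regressing Y on A and M gives M the coefficient b = Var(S)/[Var(S) + Var(e₂)], and arm the coefficient −b·d. That is a spurious arm effect whenever zinc shifts activation (d ≠ 0).

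**The case against.** The strongest reply has four parts.

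*The correlation is not the only source of evidence.* Task 3.1 covers both randomised groups and Task 3.2 uses assigned mouse diets; each gives a zinc contrast that does not arise from inflammation. This stands. A reader might infer that no arm difference in expression could be attributed to zinc. The documents do not support that. A difference between randomised arms is caused by zinc, apart from chance and dropout, even if it acts through cell mix; only the per-cell interpretation stays open. But the stated correlation with serum zinc is not described as using these contrasts.

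*The premise is partly undocumented.* No passage shows that PBMC composition changes during COVID-19. The background says transporters vary between tissues, not between blood cell types, and its metallothionein evidence comes from cancer and chronic infection. This also stands, and it limits the claim to what can happen.

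*A diagnostic need only predict.* This does not answer the point. D4 is meant to report nutritional zinc status, and a gene linked to serum zinc only through inflammation would not do so.

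*The data for adjustment are incomplete.* This stands. The flow panel names T-cell markers only, no CBC differential is specified, and Task 1.2.2 gives visit times for activation and exhaustion but not for the subset fractions. It also stimulates T cells with spike peptides, so its activation readout may not describe the cells used for RT-PCR.

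**Conclusion.** The concern holds for the expression-versus-serum-zinc correlation. As written, that analysis can name a gene as a zinc-status reporter when it marks cell mix, cell state or inflammation. The direction of the problem rests on the plan's own statements. Its size does not: the simulated rates run from near the nominal 5% to well above it, and the expression ratios and correlations behind them are assumptions.

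A reader might go further and conclude that cell shifts will be read as zinc markers. The documents support only that they can be. That the assay is bulk is itself an inference from the absence of a sorting step, though the natural one.

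The objective is exploratory and lies outside the trial's primary, secondary and safety endpoints. The point merits a change because a named clinical deliverable rests on it and a better analysis can be built largely from planned data.

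**What to change.** **Serum-zinc analysis (Objective 3, Task 3.1).** Beside the simple correlation, report a regression of log expression on serum zinc, adjusted for same-visit values of:
- CRP or IL-6;
- CD3 fraction and CD4:CD8 ratio from the Task 1.2.2 panel;
- an exhaustion marker (PD-1 or Tim-3) from that panel;
- the monocyte:lymphocyte ratio, if the CBC includes a differential.

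Name a gene as a candidate reporter of zinc status only if the association persists. State that adjustment is partial.

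**Between-arm comparison of expression.** Keep it unadjusted for post-randomisation composition or activation as the main result. Show any composition-adjusted version only as a descriptive per-cell reading.

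**Sampling.** Task 1.1.1 lists PBMCs only at Visits 3 and 4, whereas Tasks 1.2.2 and 3.1 need them at admission. These sections must be reconciled, or the admission analysis has no documented sample.

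**Cost.** Up to five covariates in about 54 to 60 patients. On the partial-correlation scale with n = 54, the smallest detectable value moves from 0.37 to tanh[2.8016/√(54 − 3 − 5)] = 0.39. The larger cost is interpretive. The background says zinc can itself lower IL-6, so adjusting for IL-6 may remove some true zinc signal. That is why both versions should be shown, and why a gene that fails the adjusted test should not be reported as unrelated to zinc.
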